12.3 ASSESSMENT OF INTENSITY

The Investigator should rate the intensity of any AE as follows:
Mild: The AE does not interfere with the subject's usual function.
Moderate: The AE interferes to some extent with the subject's usual function.
Severe: The AE interferes significantly with the subject's usual function.

12.4 ASSESSMENT OF CAUSALITY

The Investigator shall judge whether or not, in his/her opinion, the AE is associated with the study medication. When stating the causality, the following nomenclature should be used:

Unrelated: There is little or no chance that the study medication caused the AE. Possibly related: The association of the AE with the study medication is unknown, however, the AE is not clearly due to another condition.

Probably related: A reasonable temporal association exists between the AE and the study medication. Based on the Investigator's clinical experience, the association of the AE with the study treatment seems likely.

12.5 DEFINITION OF SERIOUS ADVERSE EVENTS

A serious AE is any untoward medical occurrence that at any dose:

- Results in death.
- If life threatening at the time of the event.
- Requires inpatient hospitalisation
- Requires prolongation of existing hospitalisation.
- Results in persistent or significant disability/incapacity.
- Is a congenital anomaly/birth defect.

Medical and scientific judgment should be exercised in deciding whether expedited reporting is appropriate in other situations, such as important medical events that may not be immediately life-threatening or result in death or hospitalization, but may jeopardize the patient or may require intervention to prevent one of the other Protocol version 2.3 2021-06-04

outcomes listed in the definition above. These also should usually be considered serious.

Also serious events which could be associated with the study procedures (rather than with the study medication) will be reported as SAEs, even if occurring outside the treatment period.

Under this protocol, the following events will not be considered as an SAE and should not be entered on the SAE form:

Elective hospital admission

Pre-planned hospitalizations for diagnostic, therapeutic, or surgical procedures for a pre-existing condition that did not worsen during the course of a clinical study. These pre-planned hospitalizations and the underlying conditions must be entered on the medical history form.

12.6 REPORTING OF SAEs, SUSARs and DSUR

The reporting by the Investigator to the Sponsor shall cover all SAEs (whether or not considered as related to the study treatment), including their intensity and cause. The initial report should be sent within 24 h after becoming aware of the occurrence of the event, using a Serious Adverse Event Report Form. The SAE report forms must be sent via e-mail to the Sponsor (see contact details below). If additional information is required, a follow-up report should be sent as soon as possible within another 4 days.

Sponsor: [name]	E-mail:[contact]
-------------------------------	---

If the initial SAE report is incomplete it should as far as possible be supplemented by detailed information on diagnosis/symptoms, the relationship with the start of treatment and the latest dose taken and any further relevant data.

The Investigator should also inform the Sponsor about other safety problems such as:

Increased incidence and/or severity of AEs possibly or probably related to the study medication

If a participant discontinued the study because of an in-treatment SAE, this should be noted:

- On the SAE form by marking "dosing stopped" under "action taken"
- On the last visit CRF by marking "(serious) adverse event" as the reason for discontinuation

Suspected, Unexpected Serious Adverse Reactions (SUSARs) that are fatal or life threatening shall be reported to the MPA and the ERB as soon as possible and at the latest within 7 calendar days from the first knowledge by the Sponsor. The report shall as far as possible be supplemented by additional information, but at the latest within a further 8 calendar days. It is the responsibility by the sponsor to report SUSAR to the MPA and ERB.

The reporting of other SUSARs to the MPA ad ERB shall be done as soon as possible, but not later than 15 calendar days after the first knowledge by the sponsor.

CIOMS forms will be used for submission to MPA, who will be responsible for the electronic reporting into EudraVigilance.

Sponsor should once a year during the study report safety issues including SAEs to the MPA and ERB by a Development Safety Update Report (DSUR).

12.7 FOLLOW-UP OF ADVERSE EVENTS AND SERIOUS ADVERSE EVENTS

All (S)AEs will be followed until they have abated, or until a stable situation has been reached. Depending on the event, follow up may require additional tests or medical procedures as indicated, and/or referral to the general physician or a specialist.

12.8 PROCEDURES IN CASE OF MEDICAL EMERGENCY

The Investigator should ensure that there are procedures and expertise available at the study center to cope with emergencies during the study. The Coordinating Investigator must be informed when a code has been broken. Code envelopes will be distributed to the centers in conjunction with distribution of the study drug. The envelopes will be stored at the clinic in case codes need to be broken for safety reasons.

There is also a possibility to contact the coordinating center where the complete code list will be stored. The persons listed have access to the code list, only one of them needs to be contacted:

[name] [name], PhD (co-ordinating Investigator) Center for Clinical Research (CKF) Dalarna [name], Sweden [contact] [contact] E-mail: [contact]

or

[name], PhD-student (co-investigator) Center for Clinical Research (CKF) Dalarna [name], Sweden [contact] [contact] E-mail address: [contact]

or

[name] (administrative staff) Center for Clinical Research (CKF) Dalarna [name], Sweden [contact] E-mail: [contact]

or

[name] (administrative staff) Center for Clinical Research (CKF) Dalarna [name], Sweden [contact] E-mail: [contact]

At least one of these persons will always be available during the whole study period.

12.9 LABORATORY ASSESSMENTS

Safety laboratory assessments (white and red blood cells, CRP, electrolytes and glucose) will be performed at admission according to clinical practice. However, no laboratory data will be collected in the study.

13 STATISTICS AND DATA MANAGEMENT

13.1 DATA MANAGEMENT

All data collected in this study will be recorded in CRFs. Data will be entered by the Investigators and/or their delegated staff. Data captured via the CRF will be entered into a database at Center for Clinical Research Dalarna. A copy of each CRF will be retained at the study centre for at least 10 years following completion of the study depending on the applicable regulations.

Prior to the start of the clinical study the Investigator will complete a Signature and Delegation Log showing the names of persons who are authorized to enter or change data in the CRFs.

Signing end of the study is considered to be the final authorization of the CRF; it must be signed and dated by one of the Investigators. The signature is a guarantee that (s)he has reviewed the CRF and certifies them to be complete and accurate.

Monitoring by a Sponsor's representative will be performed to ensure the safety of the human subjects, the quality of data, its scientific integrity and compliance with the applicable guidelines and regulations. Both representatives of the Sponsor and relevant authorities must have access to all study data and documents at the clinic at any time.

The Sponsor will not collect data of subjects who are not randomised into the study (i.e. screening failures). All subjects asked to participate will be listed on a screening list, which will be filed in the Investigator Study File, and if a subject is not randomized, the reason for that has to be registered on the list. A copy of the screening list will be collected by the Sponsor.

Children not being eligible for enrolment will be registered on the screening list for gender, age and reason for exclusion.

13.2 STATISTICAL ANALYSIS

The statistical methods will be described in detail in a statistical analysis plan (SAP) that will be finalized and approved before data base lock is performed. Statistical testing may be undertaken for hypothesis generating purposes, using two-sided tests and 5% alpha level, unless otherwise stated.

Data will be presented by treatment group (prednisolone/placebo). Graphical methods may be used wherever it is regarded as appropriate.

The last pre-administration observation will be used as the baseline value for calculating post-administration changes from baseline. All data obtained on the CRF Protocol version 2.3_2021-06-04

and entered into the database will be provided in separate data listings showing individual subject values. Tabulations of summary statistics, graphical presentations, and listings will be performed by the UCR statistician. All statistical calculations will be performed using SAS[®] version 9.4 or later (SAS Institute Inc., Cary, NC, USA) or SPSS statistics, version 21 (IBM Corporation, USA).

Intention-to-treat will be applied when analyzing results from the primary outcome. Comparisons between groups for dichotomous endpoints (recovery/no recovery) will be performed using Fisher's exact test and for categorical endpoints (scale) using Mann-Whitney U-test. For correlations between scales, Pearson's correlation test, or Cohen's kappa if appropriate, will be used. When predicting recovery at 1 month to 12 months, diagnostic performance will be calculated on recovery defined as House-Brackmann grade 1. Analysis of early predictors will be performed to understand variance of subgroups. Furthermore, logistic regression analysis will be used to evaluate recovery in relation to baseline data.

Study patients that have been screened but not received any study medication, will be considered as screen failures and will not be included in the study database.

13.3 DETERMINATION OF SAMPLE SIZE

Power for the FACE study is calculated on the primary end-point (number of patients with total recovery from the facial nerve palsy in each intervention group, measured by House-Brackmann grade 1 at 12 months follow-up). A difference of 10% of the total recovery rate between groups (90% versus 80%) is estimated from earlier non-RCT treatment studies (3, 15) and used for calculations of sample size. A p-value less than 0.05, a power of 0.80 and a calculated portion of patients not taking part of the study follow-up is included in the analysis.

A sample size of 500 patients need to be included in the FACE study according to this power analysis. No minimum number of included patients at one single site is determined.

14 DIRECT ACCESS TO SOURCE DATA/DOCUMENTS

The Investigators/institutions will permit study-related monitoring, audits, review and regulatory inspections, providing access to source data/hospital records. Sponsor verifies that each patient has consented in writing to direct access to the original source data/hospital records by the use of written patient information and signed Informed Consent.

15 QUALITY CONTROL AND QUALITY ASSURANCE

15.1 SOURCE DATA

The following minimum amount of information should be recorded in the hospital records:

Study

- Study title
- Aim of the study
- Randomization number
- Subject identification
- Date when signed Informed Consent was obtained
- Diagnosis
- Fulfillment of eligibility criteria
- Visit dates
- Concomitant medications
- Any AEs
- Specification of the subject's cessation in the study
- Specification of the subject's outcome in the study
- Specification of study treatment (after code break at study end)

Gradings by House-Brackmann and Sunnybrook, as well as information about Facial Clinimetric Evaluation Scale, Facial Disability Index and Synkinesis Assessment Questionnaire will be reported directly in the CRF as source data.

15.2 MONITORING

In accordance with the principles of Good Clinical Practice (GCP), monitoring of the study will be arranged by the Sponsor. During the study, the Monitor will have regular contacts with the study centers, including visits to ensure that the study is conducted and documented properly in compliance with the protocol, GCP and applicable regulatory requirements.

The study nurse will that ensure that accountability of study medication is performed and documented in an accountability log. The monitor will review source documents for verification of consistency with the data recorded in the CRFs. The Monitor will

also provide information and support to the Investigator(s). The monitoring work is described in a monitoring plan.

The study center may also be subject to quality assurance audit by the Sponsor as well as inspection by the MPA. The Investigator and other responsible personnel must be available during the monitoring visits, audits and inspections and should devote sufficient time to these processes.

The Investigator and study staff should provide a curriculum vitae (CV) or equivalent documentation of suitability to be responsible for the study. All Investigators and other responsible personnel should be listed together with their function in the study on the signature and delegation list.

15.3 DATA SAFETY MONITORING BOARD

An independent data safety monitoring board (DSMB) will be engaged, including 2-3 members. These member(s) will be chosen from having appropriate scientific knowledge in the field.

The DSMB will evaluate safety data after the first 50 patients have completed the study. The next safety evaluations will occur when 200 and 400 patients have been included. There is always a possibility to have more safety evaluations if found needed. A DSMB charter will be written for the members to outline the working procedures and their duties.

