5.2 STUDY TIME TABLE

Study planning 2017-2018.

Patient inclusion 2019-2023 with follow-up until 2024

Results and publishing 2025-2026

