The study medication including instructions about route of administration and dosage for the specific child will be distributed at the baseline visit. CRFs will be completed by the investigator or study nurse.

One week ±3 days telephone call and two weeks ±3 days telephone call

After one and two weeks, the study nurse will call the child and/or parents/guardians to follow up that study medication is taken according to instructions and to check whether any AEs have occurred. Bottles with remaining study medication will be returned after end of treatment for accountability check. Safety is followed-up by asking for AEs. CRFs will be completed by the study nurse.

One month ± 5 days and 12 months ±2 weeks follow-up visits

After 1 month and 12 months, the child with parents/guardians come to a follow-up at the pediatric or ENT-clinic. Grading of the facial nerve palsy with House-Brackmann and Sunnybrook will be performed. Safety followed-up by asking for adverse events. Also concomitant medications will be updated, if applicable. CRF's will be completed at 1 month and at 12 months by the investigator or study nurse.

The child and the parents/guardians will complete the Facial Clinimetric Evaluation (FaCE) scale, the Facial Disability Index (FDI) at 1 and 12 months follow-up and the Synkinesis Assessment Questionnaire (SAQ) at the 12 months follow-up.

Complementary treatment (for example physical therapy or massage) is asked for at the 12 months follow-up. If the patient has a moderate – severe persistent facial nerve palsy, a visit at an ENT-specialist will be arranged for further evaluation.

End of the study is defined as completed at the 12-months follow-up visit for the last included patient (LSLV). An end-of-the-study CRF for each participant will be completed by the Principal Investigator. The Medical Products Agency and the Regional Ethical Review Board will be informed within 90 days from the date of LSLV.

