10.9 CONTINUATION OF TREATMENT

After 10 days treatment stops. No further treatment will replace the study medication.

Concomitant therapy (e.g. antibiotics 10-14 days, se 10.6) will be finished as prescribed by the responsible pediatrician.

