## 9. Determination of sample size

Sample size for the FACE study is calculated on the primary outcome (i.e. number (%)) of patients with total recover of the facial nerve palsy in each intervention group, measured by House-Brackmann grade 1, at 12 months follow-up). An 10% difference of the total recovery rate between groups (80% in placebo group versus 90% in prednisolone group) is an estimation from earlier non-RCT studies, interviews with children/parents (unpublished data) and a test of two independent proportions for estimation of the minimal relevant clinical improvement (MRC). To show that such a difference is significant ( $p < 0.05$ , two-sided test) with 80 % power, a total of 430 patients are needed. However, due to the uncertainty in the assumptions and to that a portion (10%) of patients not taking part of the study follow-up, 500 patients will be included in the FACE study (250 in each group).

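### The first scheduled DSMB review waits for 50 children to finish 12 months after a 10-day course; about 150 to 175 would be enrolled by then

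*Protocol*

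**What the plan says.** Protocol 15.3 schedules three DSMB safety evaluations. For the first: "The DSMB will evaluate safety data after the first 50 patients have completed the study". For the other two: "The next safety evaluations will occur when 200 and 400 patients have been included". It adds: "There is always a possibility to have more safety evaluations if found needed", with no trigger for such extra reviews, and says that a charter will set out working procedures.

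Completion is not defined for the individual child. The last visit in Protocol 8.3 is at 12 months ± 2 weeks, and Protocol 8.2 ties the end of the trial to the same visit: "End of the study is defined as completed at the 12-months follow-up visit for the last included patient (LSLV". Month 12 is therefore the natural reading.

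On exposure, Protocol 10.9 says: "After 10 days treatment stops. No further treatment will replace the study medication". Under Protocol 8.3, adverse events are asked about at 1 week, 2 weeks, 1 month and 12 months. Protocol 12.9 places the safety laboratory tests at admission and says that no laboratory data are collected for the study.

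**The concern.** An early safety review exists to protect the children enrolled after it, so its value depends on how few are enrolled when it happens. Here the review meant to be earliest carries the slowest trigger. Waiting from month 1 to month 12 adds one scheduled adverse-event contact per child, about 11 months after the last dose. The short-course effects named in the protocol's own risk analysis (16.2: mood, sleep, nausea, vomiting, infection) would mostly be expected around the treatment period.

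The mixed triggers also space the reviews badly. There is no scheduled DSMB review for well over a year, and then two come close together. Protocol 5 states that no RCT of cortisone has been done in children with this condition, which is a reason to want the first look early.

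**Working it through.** The documents give no figure for enrolment at the first review, so there is none to reproduce. It follows from the plan's own enrolment target and calendar.

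**Inputs**
- Planned enrolment: "500 patients will be included in the FACE study (250 in each group" (SAP section 9), hence about half on each treatment.
- Accrual period: "Patient inclusion 2019-2023 with follow-up until 2024" (Protocol 5.2). This is 5 years if both end years are full; I take 4 years as the lower bound. Even accrual is an assumption.
- First trigger: 50 children at month 12. Later triggers: 200 and 400 included.
- Loss to follow-up: 10% (SAP section 9). Visit windows: ± 2 weeks at 12 months, ± 5 days at 1 month (Protocol 8.3).

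**Enrolment at the first review.** With Y years of accrual, the annual rate is r = 500/Y. The 50th child enters at 50/r years and completes one year later, so enrolment by then is r × (50/r + 1) = 50 + r.
- 5 years: r = 100; review at 0.5 + 1 = 1.5 years (month 18); enrolled 50 + 100 = **150**, about 75 on prednisolone.
- 4 years: r = 125; review at 0.4 + 1 = 1.4 years (month 16.8); enrolled 50 + 125 = **175**, about 88 on prednisolone.

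**Sensitivity**

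| Scenario | 5 years | 4 years |
|---|---|---|
| Even accrual, visit exactly at 12 months | 150 | 175 |
| 12-month visit 2 weeks early or late | 146 to 154 | 170 to 180 |
| 10% loss (50/0.9 = 55.6 enrolled to yield 50 completers) | 156 | 181 |
| 10% loss and visit window | 152 to 159 | 176 to 185 |
| Linear ramp-up over 1 year | 161 | 191 |
| Linear ramp-up over 2 years | 158 | 183 |

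For a ramp of R years, the full rate is 500/(Y − R/2), and cumulative enrolment during the ramp is rate × t²/(2R). Example with Y = 5, R = 1: rate 111.1; the 50th child enters at √(2 × 50/111.1) = 0.949 years; enrolment one year later is 111.1 × (1.949 − 0.5) = 161. The overall range is about 146 to 191, so 150 lies near its lower end.

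**Distance to the next review** (even accrual, no loss). The 200th inclusion falls at 200/100 = 2 years (month 24) or 200/125 = 1.6 years (month 19.2). The gaps are 24 − 18 = 6 months and 19.2 − 16.8 = 2.4 months.

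**Follow-up at the 200-inclusion review.** Children with a full 12 months by then number 100 × (2 − 1) = 100, or 125 × (1.6 − 1) = 75, out of 200. The second review therefore already accepts partial follow-up for half or more of the children.

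**With a 1-month trigger.** Enrolment is 50 + r/12 = 58 (5 years) or 60 (4 years). At the late edge of the visit window, taken as 35 days, it is 50 + r × 35/365.25 = 60 or 62. The range is about 58 to 62. The reduction is 150 − 58 = 92 or 175 − 60 = 115 children, of whom about 46 or 57 would be on prednisolone.

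**The case against.** A reader might infer that nobody looks at safety until 150 children are in. The documents do not support that. Protocol 12.6 sends every SAE to the sponsor within 24 hours, asks investigators to report increases in the incidence or severity of related events, sends SUSARs to the MPA and ERB within 7 or 15 days, and requires a yearly DSUR. Protocol 20.4 lists an unexpectedly high proportion of related events as a ground for stopping. Protocol 15.3 allows extra DSMB evaluations, and the charter may schedule some. All of this stands. The gap concerns only the first scheduled independent DSMB review. These safeguards do not close it: extra reviews have no stated trigger, and the stopping ground has no threshold.

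A reader might also infer that the first review is redundant. That is too strong: at 100 children per year it precedes the next one by six months and 50 children.

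The remaining objections are:
- The safety endpoint counts related events over 12 months (Protocol 7.2), so a first look at complete records is a defensible choice. But the later reviews do not insist on complete records, and no reason is given for insisting at the first.
- A look at 50 children has little power. With about 25 on prednisolone and the rates in Protocol 16.2, one expects 25 × 4.3% to 5.4%, or 1.1 to 1.4 minor events, and fewer than 25 × 1% = 0.25 infection events. This is true at either time, and it limits how much the change can gain.
- The protocol version is dated June 2021. At 100 per year from the start of 2019, the 50th completion would have fallen in mid-2020. The documents do not report actual accrual, so this cannot be settled; the plan is assessed as written.

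**Conclusion.** The point holds as a matter of timing. The first scheduled independent DSMB review is tied to 12-month completion after a 10-day course, while the later reviews are tied to inclusion. About 150 to 175 children (146 to 191 across the scenarios), roughly half on prednisolone, would be enrolled before it.

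This rests on three things: 500 children accruing over 4 to 5 years, completion meaning the 12-month visit, and no earlier review in the charter, which was not available. No harm from the delay is shown or quantified, and the protocol expects a mild short-course profile. This is a cheap improvement to oversight and not a defect that threatens the trial.

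**What to change.** Amend Protocol 15.3, and align the DSMB charter, so that the first evaluation takes place when the first 50 randomised children have reached their 1-month visit. Keep the evaluations at 200 and 400 included. If the charter already provides an earlier review, 15.3 should say so.

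The cost is one sentence in each document. The number of meetings is unchanged, no extra data are collected, and the reviews concern safety only.

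The downside is that events between 1 and 12 months in the first 50 children would be seen at the 200-inclusion review. In every scenario above, the 50th completion comes before the 200th inclusion, so that review would still have their full follow-up; under even accrual without loss it comes about 2.4 to 6 months later than the present first review.
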